4.1. Summary of Study Design

Study J2T-MC-KGBP (KGBP) is an open-label, phase 3b study, which is 24 weeks in treatment duration. The study is designed to evaluate the safety and efficacy of lebrikizumab in male and female adult and adolescent participants with skin of color and moderate-to-severe AD.

Study Periods

This trial has 4 study periods:

- Screening (Visit 1: \leq 30 days prior to baseline)
- Treatment (Visits 2-9: 24 weeks)
- Safety follow-up (Visit 801: at Week 34 or approximately 12 weeks after last treatment)
- Continued Access (Visits 501, 502, and 503)

Participants who enroll into KGBP Protocol Addendum 3 will move directly into the Continued Access Period after completing the 24-week treatment period. Such participants will not complete Visit 801. A post-treatment follow-up visit (V901) will occur approximately 12 weeks post the last dose at the end of the Continued Access Period for the participants who do not move to commercial lebrikizumab or who discontinued early from the Continued Access Period. Please refer to KGBP Protocol Addendum 3 for more information.

Visit Types

Study visits at Week 12 (Visit 6) and Week 20 (Visit 8) will be performed virtually, that is, via telephone or telemedicine tools.

All other visits will be conducted at the clinical trial site.

Dosing

During the 24-week Treatment Period, approximately 80 participants will receive treatment:

- 500 mg subcutaneous (SC) loading dose at baseline and Week 2, followed by 250 mg SC Q2W until Week 16.
- Responders, defined as achieving IGA (0,1) or EASI-75 at Week 16, will receive Q4W dosing and will administer study intervention at Week 20.
- Inadequate responders at Week 16 will receive Q2W dosing and will administer study intervention at Weeks 18, 20, and 22.

During the Continued Access Period, eligible participants will continue lebrikizumab on the same dosing regimen (Q2W or Q4W) they were assigned at Week 16. Please refer to KGBP Protocol Addendum 3 for more information.

The study population is described in Section [5.1.1](#).

[figure not shown]
The efficacy and safety assessments are described in Sections 5.11 and 5.13 respectively.

4.1.1 Number of Participants

Approximately 80 participants will be enrolled to study intervention. Because the inclusion of Black and African American patients is historically limited in clinical trials and given the focus of skin of color in this study, the majority of the patients in this study will be of Black or African American race (approximately 55 participants). The remainder of the participants may be of any race other than White, with enrollment of up to 10% Asian participants. Patients will be evaluated for study eligibility before the baseline visit (Day 1).

4.1.2 Schema

Figure KGBP.4.1

Abbreviations: EASI = Eczema Area and Severity Index; IGA = Investigator's Global Assessment; n = number; Q2W = once every 2 weeks; Q4W = once every 4 weeks; SC = subcutaneous; W = week.

^a Weeks 12 and 20 are phone visits.

^b 30-day screening window.

^c Lebrikizumab loading dose of 500 mg SC will be administered at baseline and Week 2.

^d Responders: Participants who reach IGA 0 or 1 (clear or almost clear) or a 75% reduction in the EASI score from baseline (EASI-75). Inadequate responders are participants who do not reach these criteria.

^e The safety follow-up visit will occur approximately 12 weeks after last study intervention injection.

^f The planned maximum duration of Continued Access treatment will vary for each participant enrolled into KGBP Protocol Addendum 3 and will end if and when the participant meets criteria for discontinuation of study intervention or discontinuation from the study. Participants may remain in the Continued Access Period as long as these criteria for discontinuation are not met and until the sponsor stops the study and addendum.

^g Participants in the Continued Access Period will receive the same dose they were taking during Weeks 16 to 24 of the Treatment Period.

4.2. Determination of Sample Size

Based on available data, the anticipated EASI-75 response rate is approximately 50%. A total sample size of 80 enrolled participants will provide >95% probability that the half-width of the 2-sided 90% CI of the EASI-75 response rate is at most 10%.

Example point estimates for EASI-75 response rates and corresponding 2-sided 90% CIs based on the Wilson Score method for a sample size of 80 participants are summarized in the table below. The CIs are provided as reference rather than a basis of any decision criteria.

Table 4.2 Estimated 90% CI with Sample Size of 80 Participants

Example Point Estimates	Lower Bound of 90% CI	Upper Bound of 90% CI
40%	31.46%	49.19%
45%	36.16%	54.16%
50%	40.96%	59.04%
55%	45.84%	63.84%
60%	50.81%	68.54%
65%	55.87%	73.15%
70%	61.03%	77.66%

4.3. Method of Assignment to Treatment

This is an open-label study. All enrolled patients will be assigned to 250-mg lebrikizumab Q2W at the baseline visit. At Week 16, patients will be assigned to 250-mg lebrikizumab Q2W or 250-mg lebrikizumab Q4W based on their IGA or EASI score.

5. A Priori Statistical Methods

5.1. General Considerations

Statistical analysis of this study will be the responsibility of ICON. The latest version of the MedDRA will be used.

Summaries from assessment of endpoints described in the protocol are planned to be included in a CSR. Summaries for key safety data are also planned to be included in the CSR. Results from additional efficacy summaries and other safety summaries may also be provided in the CSR as deemed appropriate.

Any change to the data analysis methods described in the protocol will require a protocol amendment ONLY if it changes a principal feature of the protocol. Any other change to the data analysis methods described in the protocol and the justification for making the change will be described in the CSR.

All statistical processing will be performed using SAS® 9.4 unless otherwise stated.

The schedule of visits and procedures outlined in the protocol specifies the allowable windows for assessments. Assessments performed outside these windows will not be excluded from any summaries, unless specified otherwise.

5.1.1 Analysis Populations

Analysis populations are defined in Table KGBP.5.1 along with the analyses they will be used to conduct. The number of patients included in each population will be summarized.

Table KGBP.5.1.1 Analysis Populations

Population	Description
All Entered Patients	All patients who signed informed consent. Patient flow will be summarized.
Intent-to-Treat (ITT) Population	All enrolled patients according to their planned intervention. Unless otherwise specified, efficacy and health outcomes analyses for Weeks 0 to 16 of the Treatment Period will be conducted on this population.
Safety Population	All enrolled patients who received at least 1 confirmed dose of lebrikizumab 250 mg. Safety analyses will be conducted on this population.
Treatment Period II Population	All enrolled patients who received at least 1 confirmed dose of lebrikizumab 250 mg during Weeks 16 to 24 of the Treatment Period. Unless otherwise specified, efficacy and health outcomes analyses for Weeks 16 to 24 of the Treatment Period will be conducted on this population.

5.1.2 General Considerations for Analyses

All analyses will be descriptive. Frequencies, percentages, and 90% Wilson-Score CIs for percentages will be reported for discrete efficacy endpoints. Mean, standard deviation, minimum, Q1, median, Q3, maximum, and the number of participants will be reported for continuous

efficacy endpoints. AEs, discontinuation, and other categorical safety data will be summarized using frequencies and percentages. Continuous vital signs, body weight, and other continuous safety variables including laboratory variables will be summarized descriptively as well.

Baseline

Baseline will be defined as the last available value before the first injection for efficacy and health outcome analyses. In most cases, this will be the measure recorded at the baseline visit (Day 1). If the patient does not take any injection, the last available value on or prior to treatment assignment date will be used. Change from baseline will be calculated as the visit value of interest minus the baseline value.

For Pruritus Numeric Rating Scale (NRS), Skin Pain NRS, and Sleep-Loss due to Pruritus collected via eDiary, the baseline period is the 7-day window prior to the first injection. A patient must have responses on at least 4 of 7 days to calculate a baseline weekly mean. If a patient has 3 or fewer responses, the baseline mean value will be considered missing.

For the safety analyses, the following baselines will be used. For safety analyses using a baseline period, the baseline period is defined as the time from the screening visit to the date/time of the first injection.

- TEAEs: baseline will be all results recorded during the baseline period.
- Treatment-emergent abnormal laboratory and vital signs results: baseline will be all results recorded during the baseline period.
- Change from baseline to last post-baseline observation or to each scheduled postbaseline visit for laboratory and vital signs results: baseline will be the last scheduled non-missing assessment recorded during the baseline period.

5.2 Primary and Supportive Estimands

There will be five estimands addressing different clinical questions of interest and intercurrent events for the primary and secondary endpoints.

5.2.1. Primary Estimand for the Primary Endpoint

The primary estimand for the primary endpoint represents the primary clinical question of interest: What is the intervention effect in percentage of participants achieving at least 75% improvement from baseline in Eczema Area and Severity Index (EASI) after 16 weeks of lebrikizumab 250 mg Q2W intervention in participants with skin of color and moderate-to-severe AD who remain on study treatment until Week 16?

The primary estimand for the primary endpoint is described by the following attributes:

- A. Population: participants with skin of color and moderate-to-severe AD who remain on study treatment until Week 16.
- B. Endpoint: whether participants achieve at least 75% improvement from baseline in EASI at Week 16.

- C. Intercurrent events: There are no intercurrent events for this population since participants who initiate rescue medication are discontinued from the study and hence study treatment. Therefore, participants who stay on study treatment through Week 16 will not have an intercurrent event such as initiating rescue medication or permanently discontinuing treatment.
- D. Population-level summary: percentage of participants achieving EASI-75 response at Week 16.

5.2.2. Supportive Estimands for the Primary Endpoint

There are two supportive estimands for the primary endpoint. The first is a hybrid estimand representing the following clinical question of interest: What is the intervention effect in percentage of participants achieving at least 75% improvement from baseline in Eczema Area and Severity Index (EASI) after 16 weeks of lebrikizumab 250 mg Q2W intervention in participants with skin of color and moderate-to-severe AD if all participants adhered to treatment except those who discontinued due to lack of efficacy?

This estimand is described by the following attributes:

- A. Population: participants with skin-of-color and moderate-to-severe AD.
- B. Endpoint: whether participants achieve at least 75% improvement from baseline in EASI at Week 16.
- C. Intercurrent events (ICEs): One ICE, permanent treatment discontinuation, is considered by this estimand as follows:
 - a. Participants who discontinue treatment due to lack of efficacy prior to Week 16 will be considered as treatment failures, i.e. non-responders, after the ICE. Therefore, a composite strategy is used for this type of ICE.
 - b. For participants who discontinue treatment due to reasons other than lack of efficacy prior to Week 16, a hypothetical strategy will be used to estimate what the treatment effect would have been if subjects continued with treatment. Therefore, a hypothetical strategy is used for this type of ICE.
- D. Population-level summary: percentage of participants achieving EASI-75 response at Week 16.

The second supportive estimand for the primary endpoint is a hypothetical estimand representing the following clinical question of interest: What is the intervention effect in percentage of participants achieving at least 75% improvement from baseline in Eczema Area and Severity Index (EASI) after 16 weeks of lebrikizumab 250 mg Q2W intervention in participants with skin of color and moderate-to-severe AD if all participants adhered to treatment?

This estimand is described by the following attributes:

- A. Population: participants with skin of color and moderate-to-severe AD.
- B. Endpoint: whether participants achieve at least 75% improvement from baseline in EASI at Week 16.
- C. Intercurrent events (ICEs): One ICE, permanent treatment discontinuation, is considered by this estimand as follows:

- a. For participants who discontinue treatment prior to Week 16, a hypothetical strategy will be used to estimate what the treatment effect would have been if all subjects continued with treatment. Therefore, a hypothetical strategy is used for this type of ICE.
- D. Population-level summary: percentage of participants achieving EASI-75 response at Week 16.

5.2.3. *Estimands for Secondary Endpoints at Week 16*

The primary estimand for the primary endpoint will be applied to all secondary endpoints at Week 16. The supportive estimands for the primary endpoint will also be applied to all secondary endpoints at Week 16.

5.2.4. *Estimands for Secondary Endpoints at Week 24*

The primary estimand for the primary endpoint will be applied to all secondary endpoints at Week 24. There are two supportive estimands for secondary endpoints at Week 24. The first is a hybrid estimand representing the following clinical question of interest: What is the intervention effect in successful responses or means after 24 weeks of lebrikizumab intervention in participants with skin of color and moderate-to-severe AD if all participants adhered to treatment except those who discontinued due to lack of efficacy?

This estimand is described by the following attributes:

- A. Population: Treatment Period II population as described in Section 5.1.1.
- B. Endpoint: apply to all secondary endpoints at Week 24.
- C. Intercurrent events (ICEs): One ICE, permanent treatment discontinuation, is considered by this estimand as follows:
 - a. Participants who discontinue treatment due to lack of efficacy after Week 16 will be considered as treatment failures, i.e. non-responders, after the ICE. Therefore, a composite strategy is used for this type of ICE.
 - b. For participants who discontinue treatment due to reasons other than lack of efficacy after Week 16, a hypothetical strategy will be used to estimate what the treatment effect would have been if subjects continued with treatment. Therefore, a hypothetical strategy is used for this type of ICE.
- D. Population-level summary: percentage of successful responses or means at Week 24.

The second supportive estimand for secondary endpoints at Week 24 is a hypothetical estimand representing the following clinical question of interest: What is the intervention effect in successful responses or means after 24 weeks of lebrikizumab 250 mg Q2W intervention in participants with skin of color and moderate-to-severe AD if all participants adhered to treatment?

This estimand is described by the following attributes:

- A. Population: Treatment Period II population as described in Section 5.1.1.

- B. Endpoint: apply to all secondary endpoints at Week 24.
- C. Intercurrent events (ICEs): One ICE, permanent treatment discontinuation, is considered by this estimand as follows:
 - a. For participants who discontinue treatment after Week 16, a hypothetical strategy will be used to estimate what the treatment effect would have been if all subjects continued with treatment. Therefore, a hypothetical strategy is used for this type of ICE.
- D. Population-level summary: Population-level summary: percentage of successful responses or means at Week 24.

Because participants who initiate rescue medication are required to discontinue from the study and hence permanently discontinue study treatment, the supportive estimands for the primary and secondary endpoints only consider permanent treatment discontinuation as an ICE.

Analytical details on how missing data including those as a result of intercurrent events will be handled can be found in Section 5.4. The following table (Table KGBP.5.3) summarizes the analytical strategies that will be conducted on the intercurrent events for the five estimands.

Table KGBP.5.3 Description of Primary and Supportive Estimands

Estimand	Population	Analysis Strategy for the ICE of Permanent Treatment Discontinuation		Missing Data Imputation Method
		Due to lack of efficacy	Due to any other reasons, including initiation of rescue medication	
Primary Estimand for the Primary Endpoint and Secondary Endpoints	ITT Population who remained on treatment	Not applicable	Not applicable	Primary analysis: as observed
Supportive Estimand for the Primary Endpoint and Secondary Endpoints at Week 16 (Hybrid)	ITT Population	Composite: Set to baseline	Hypothetical: Set to missing	MCMC-MI
Supportive Estimand for the Primary Endpoint	ITT Population	Hypothetical: Set to missing	Hypothetical: Set to missing	LOCF

and Secondary Endpoints at Week 16 (Hypothetical)				
Supportive Estimand for Secondary Endpoints at Week 24 (Hybrid)	Treatment Period II Population	Composite: Set to baseline	Hypothetical: Set to missing	MCMC-MI
Supportive Estimand for Secondary Endpoints at Week 24 (Hypothetical)	Treatment Period II Population	Hypothetical: Set to missing	Hypothetical: Set to missing	LOCF

Abbreviations: ICE = intercurrent event; LOCF = last observation carried forward; MCMC = Markov chain Monte Carlo.

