#### **6.8.5. Rescue Medicine for Atopic Dermatitis**

The goal of this Phase 3b study is to demonstrate the safety and efficacy of lebrikizumab for moderate-to-severe AD in participants with skin of color. To be consistent with real world practice, defined topical medications are allowed in this study (see Section 6.8.4). Rescue therapies may be needed if the participant experiences intolerable clinical worsening of symptoms. Escalation to high-potency topical TCS, topical JAKs, phototherapy, and/or systemic medications, including but not limited to corticosteroids, immunosuppressants, biologics, small molecules, etc., for the treatment of AD should only occur if participants do not respond adequately after at least 7 days of low- or mid-potency TCS, TCI, and/or topical PDE4 inhibitors. Any use of topical JAKs, phototherapy, and/or systemic medications will be considered Rescue Therapy. Use of high-potency TCS for more than 10 days is also considered Rescue Therapy. Participants that receive Rescue Therapy must be discontinued from the study (see Section 7.1). All rescue medication must be recorded in the CRF.

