### 7.1. Discontinuation of Study Intervention

When necessary, a participant may be permanently discontinued from study intervention. If so, the participant will remain in the study to complete procedures for an early discontinuation visit and post-treatment follow-up, if applicable, as shown in the SoA.

A participant should be permanently discontinued from study intervention if

- the participant becomes pregnant during the study
- in the opinion of the investigator, the participant should permanently discontinue the study intervention for safety reasons
- the participant develops a malignancy, except for successfully treated basal or squamous cell skin carcinoma
- the participant tests positive for HBV DNA (see Section 8.2.3)
- the participant tests positive for HCV RNA (Section 8.2.4)
- if the participant experiences a hepatic event or liver test abnormality as specified in the liver chemistry stopping criteria (see Section 7.1.1)
- the participant develops HIV infection
- the participant develops any infection that is opportunistic, such as active tuberculosis and other infections whose nature or course may suggest an immuno-compromised status
- the participant requires rescue medication treatment for symptoms of AD in the treatment period, and
- the participant has an AE or an SAE or a clinically significant change in a laboratory value that, in the opinion of the investigator, merits discontinuation of study intervention and appropriate measures being taken.

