## 7.2. Participant Discontinuation/Withdrawal from the Study

Discontinuation is expected to be uncommon.

A participant may withdraw from the study:

- at any time at the participant's own request
- at the request of the participant's designee (for example, parents or legal guardian)
- at the discretion of the investigator for safety, behavioral, compliance, or administrative reasons
- if enrolled in any other clinical study involving an investigational product, or enrolled in any other type of medical research judged not to be scientifically or medically compatible with this study, and
- if the participant, for any reason, requires treatment with a therapeutic agent that is prohibited by the protocol and has been demonstrated to be effective for treatment of the study indication. In this case, discontinuation from the study occurs prior to introduction of the new agent.

At the time of discontinuing from the study, the participant will complete procedures for an early discontinuation visit and post-treatment follow-up, if applicable, as shown in the SoA. If the participant has not already discontinued the study intervention, the participant will be permanently discontinued from the study intervention at the time of the decision to discontinue the study.

If the participant withdraws consent for disclosure of future information, the sponsor may retain and continue to use any data collected before such a withdrawal of consent. If a participant

withdraws from the study, the participant may request destruction of any samples taken and not tested, and the investigator must document this in the site study records.

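### The hybrid analyses impute discontinuations for AD rescue, which fits poorly with counting efficacy failure as non-response, and no rule settles overlap with lack of efficacy

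*SAP*

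**What the plan says.** SAP 5.2.2 defines a hybrid estimand that divides permanent discontinuation by reason. For the first group: "Participants who discontinue treatment due to lack of efficacy prior to Week 16 will be considered as treatment failures, i.e. non-responders, after the ICE". For all other reasons a hypothetical strategy applies. SAP 5.2.3 extends this to every Week 16 secondary endpoint, and SAP 5.2.4 repeats the split for Week 24: "Participants who discontinue treatment due to lack of efficacy after Week 16 will be considered as treatment failures, i.e. non-responders, after the ICE".

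Rescue is not a separate intercurrent event. SAP 5.2.4 reasons that rescue forces exit from the study, so "the supportive estimands for the primary and secondary endpoints only consider permanent treatment discontinuation as an ICE". Table KGBP.5.3, which follows, has one column for lack of efficacy and a second headed "Due to any other reasons, including initiation of rescue medication". In both hybrid rows the first column is set to baseline; the second is set to missing and imputed by MCMC-MI.

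SAP 5.4.3 applies the baseline rule to lack-of-efficacy discontinuations only, imputes whatever else is missing, and compares imputed EASI with observed baseline EASI to derive EASI-75.

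Protocol 6.8.5 says that rescue may be needed for intolerable worsening, and that escalation "should only occur if participants do not respond adequately after at least 7 days of low- or mid-potency TCS, TCI, and/or topical PDE4 inhibitors". Protocol 7.1 lists among the reasons for permanent discontinuation that "the participant requires rescue medication treatment for symptoms of AD in the treatment period".

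**The concern.** The hybrid is the one planned analysis that scores efficacy failure as non-response by rule. AD rescue, as the protocol describes it, is reasonably read as efficacy failure, although the protocol does not use the term lack of efficacy for it. The table header nevertheless places it with the discontinuations whose outcome is imputed as if treatment had continued.

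There is also an unresolved overlap. If a participant stops for AD rescue and the recorded primary reason is lack of efficacy, SAP 5.2.2 and 5.4.3 give non-response while the table header points to imputation. No precedence rule is given, so the programmer must choose. At stake is a small upward shift in the hybrid response rate and some dependence on how the reason is recorded. For continuous endpoints the choice is between the baseline value and an imputed value.

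**Working it through.** **Yardstick.** The 90% Wilson interval has half-width z√(p(1−p)/n + z²/4n²) / (1 + z²/n), with z = 1.645. For p = 0.50 and n = 80 it gives 40.96% to 59.04%, half-width 9.04 points, matching SAP Table 4.2; the other six rows also reproduce. At n = 95, the enrollment in the current protocol, the half-width is 8.32 points.

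**Size of the shift.** Let k be the number discontinued for AD rescue, N the number analyzed, and q the share of those k imputed as responders. The composite strategy scores them 0 and imputation scores them q, so the shift is 100 × k × q / N points. It is zero if all are handled as lack of efficacy.

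**Inputs.** SAP 4.2 gives N = 80 and an anticipated rate of 50%. Neither document gives k or q, and Protocol 7.2 expects discontinuation to be uncommon. I assume k = 4 or 8 (5% or 10%).

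**Ceiling.** Suppose 40 of 80 respond, no rescued participant responds, and q equals the as-observed rate:
- k = 4: q = 40/76 = 52.6%; shift = 4 × 0.526 / 80 = 2.6 points.
- k = 8: q = 40/72 = 55.6%; shift = 8 × 0.556 / 80 = 5.6 points.

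This gives rescued participants the completers' response rate, which is implausible if rescue marks a poor course.

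**Simulation of q (all inputs assumed).** 500 replicates of 80 participants, with 25 sequential normal-model imputations of EASI at Weeks 0, 2, 4, 8 and 16. Baseline EASI was lognormal (median 26, log-SD 0.4, limited to 16–72). Mean log-ratios to baseline were −0.35, −0.65, −1.05 and −1.386 (the last is a ratio of 0.25, hence about 50% EASI-75), with SDs 0.35, 0.5, 0.7 and 0.9 and correlation 0.8^|i−j| between visits. Rescue came after Week 4, either in participants from the worst third by Week 4 EASI ratio (poor responders) or in any participant. Where used, the early-discontinuation EASI was 80–120% of baseline, placed at Week 8.

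| Setting | q, k = 4 / 8 | Shift in points, k = 4 / 8 |
|---|---|---|
| Poor responders, early-discontinuation EASI used | 3.5% / 3.4% | 0.18 / 0.34 |
| Any participant, early-discontinuation EASI used | 4.7% / 4.7% | 0.24 / 0.47 |
| Poor responders, not used | 17.6% / 17.3% | 0.88 / 1.73 |
| Any participant, not used | 39.9% / 38.9% | 2.0 / 3.9 |

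The last row needs rescue unrelated to earlier response and no usable early-discontinuation score. The first three give about 0.2 to 2 points, or 0.16 to 1.6 participants of 80. At the same rescue percentages the shift in points is the same at n = 95. The protocol's Schedule of Activities includes EASI at early discontinuation, but SAP 5.4.3 does not say whether it enters the imputation.

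**The case against.** The strongest reply is that the header is itself a rule and a deliberate one. SAP Appendix 1 defines the rescue concept as therapy for AD, so the header covers AD rescue, and the two reason groups are exhaustive. This stands. A reader might infer that the SAP leaves AD rescue without any rule; it does not. The defect is that the stated rule suits the hybrid question poorly and has no precedence over, or under, the lack-of-efficacy rule.

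A reader might also infer that the roles of the analyses are reversed, because imputation can credit some rescued participants as responders where LOCF carries a poor score forward. The documents do not support that. They set no required ordering, and the contrast is largely a general property of multiple imputation against LOCF.

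It is fair, too, that the discontinuation reason list on the case report form is not in the documents. SAP 5.7 refers only to a primary reason, so how often sites would record rescue and lack of efficacy interchangeably is unknown. Protocol 7.2 adds an exit route for participants who need a prohibited effective therapy: "In this case, discontinuation from the study occurs prior to introduction of the new agent". Lack of efficacy would be a natural code there, which limits the number affected.

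Finally, the other-reasons column suits some rescue. Protocol 6.8.2 counts systemic corticosteroids given for adverse events as rescue, and imputing those is consistent with the estimand.

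**Conclusion.** The point holds as a minor one. For AD rescue, the table's handling does not match the hybrid's own purpose, and the overlap with lack of efficacy is unresolved. The textual finding needs no assumption beyond reading AD rescue as efficacy failure, which Protocol 6.8.5 makes reasonable.

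The size rests entirely on assumed rescue counts and simulation inputs. With 4 or 8 of 80 rescued, the Week 16 hybrid EASI-75 rate is plausibly raised by about 0.2 to 2 points, well inside the 9-point half-width. No Week 24 figure was computed.

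It would be wrong to conclude that the main result is at risk. The as-observed primary analysis is restricted to participants who remain on treatment, and LOCF handles both columns alike. Every analysis in the study is descriptive, with no hypothesis test.

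**What to change.** In Table KGBP.5.3 and SAP 5.2.2, 5.2.4 and 5.4.3, state for the hybrid analyses:

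- A permanent discontinuation triggered by the need for, or start of, rescue for AD is handled by the composite strategy (set to baseline, non-response), even if the recorded primary reason is not lack of efficacy. Identify it by the recorded reason for use, with the need or start at or before the discontinuation decision, or documented as its cause.
- AD therapy first started after discontinuation for an unrelated reason, such as an adverse event or pregnancy, does not trigger the rule. The time order matters because concomitant medications are collected through Visit 801.
- Rescue-class drugs given for non-AD adverse events stay in the other-reasons column.
- SAP 5.4.3 says whether the early-discontinuation EASI enters MCMC-MI.

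Report the number of AD-rescue discontinuations beside the planned summaries.

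The cost is wording in four places, one derived flag, and an indication and timing check on each rescue record, since Appendix 1 classifies rescue mainly by drug and route. Reason for use (Protocol 6.8) is already collected; discontinuation reason (SAP 5.7) and rescue use (SAP 5.10) are already tabulated. The supportive response rate may be slightly lower, and a responder who flares and needs rescue will count as a failure. Clinical management and the primary analysis do not change.
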